#### **4.3.2 Secondary Objective**

Demonstrate safety and effectiveness of the amiodarone hydrogel application during lung transplantation in preventing atrial arrhythmias during first year of transplantation.

### **4.4. ENDPOINTS**

#### **4.4.1 Primary Endpoint**

-Development of post-operative atrial fibrillation during initial hospitalization

#### **4.4.2 Secondary Endpoints**

- Length of Stay
- Development of post-operative atrial fibrillation during first year post transplant
- Thirty-day survival
- One-year Survival

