#### **3.4 RESIDUAL RISKS ASSOCIATED WITH THE DRUG UNDER INVESTIGATION, AS IDENTIFIED IN THE RISK ANALYSIS REPORT**

Due to the short half-life and one time application of the amiodarone gel, no long term residual risk is anticipated.

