#### **4.2.2 Data Collection**

Data from the prospective cohort will be collected and stored in a HIPAA compliant, encrypted and secured database. A detailed preoperative history will be obtained from the patients including: age, gender, reason for transplant, pre-transplant oxygen requirement, previous myocardial infarction, previous sternotomy, previous arrhythmia, smoking history, diabetes, stroke, hypertension. Intraoperative patient characteristics obtained will include: single lung transplant, double lung transplant, cardiopulmonary use, and ischemic time. Post-operative

patient characteristics will include: ICU duration, length of stay, post-operative atrial fibrillation during first week post-transplant, atrial fibrillation at time of discharge, atrial fibrillation at time of post-operative follow up, atrial fibrillation requiring cardioversion, atrial fibrillation requiring new anti-arrhythmic medication, asymptotic bradycardia and bradycardia requiring temporary pacemaker. Data will be collected from the subject's medical records immediately following their visits.

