### **4.3 OBJECTIVES**

#### **4.3.1 Primary Objective**

Demonstrate safety and effectiveness of the amiodarone hydrogel application during lung transplantation in preventing atrial arrhythmias during index hospital stay.

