## 14.0 STATISTICAL CONSIDERATIONS

### 14.1 STATISTICAL DESIGN, HYPOTHESES, METHOD AND ANALYTICAL PROCEDURES

This clinical study will provide data to support the safety, preliminary efficacy, and performance of the use of the Amiodarone hydrogel in preventing atrial arrhythmia during lung transplantation. The study has a treatment arm and a control arm. The control arm is the historic controls and will use the previously treated lung transplant patients at the facility. The treatment arm will use investigational amiodarone hydrogel. The study sample size calculation is based on typical regulatory criteria for a feasibility study to assess for safety and preliminary effectiveness hence it is not based on a power analysis to show statistically significant difference between the groups. However, the reported rate of early atrial fibrillation post lung transplantation is approximately 30% and assuming that the use of amiodarone gel will result in prevention of atrial fibrillation in 90% patients a sample size of 20 in each arm may have sufficient power to answer the question of preliminary effectiveness and safety.

Endpoint analysis will be on “as-treated” basis as historical control data will be used. Patients who will dropout or withdraw from the study before reaching the primary end-point will be excluded from the study and replaced by new enrollees to have at least 20 patients enrolled the study arm. The primary end-point analysis will be based on the study groups as per the protocol (treatment group vs. control groups). Subjects, who withdraw consent, will not be included in analyses.

All clinically relevant baseline and follow up variables will be tabulated. Means, medians, proportions and 95% confidence intervals will be reported. Comparisons of data collected at baseline and at follow-up will be analyzed as follows: categorical variables will be tested using contingency tables analyses (exact or chi-square approximations), and continuous variables will be tested using unpaired Student’s t-test or Wilcoxon rank-sum test, depending on variable distribution. The post-transplant AFIB was evaluated between study and control groups for overall occurrence, AFIB lasting < 24 hours and AFIB lasting > 24 hours. All the data were analyzed using SAS 9.4 software (SAS Inc., Cary, NC).

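### First-year AF includes every index-stay event, and the planned data items cannot show what happens after discharge

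*Combined protocol and SAP*

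**What the plan says.** The primary endpoint is "Development of post-operative atrial fibrillation during initial hospitalization" (section 4.4.1). The only later rhythm endpoint is "Development of post-operative atrial fibrillation during first year post transplant" (section 4.4.2). The objectives use the same two windows: "preventing atrial arrhythmias during index hospital stay" (4.3.1) and "preventing atrial arrhythmias during first year of transplantation" (4.3.2).

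Nothing starts the second window at discharge or sets aside patients who already had AF in hospital. Section 14.1 compares AF overall and by duration below or above 24 hours, with no split at discharge.

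For data capture, section 4.2.2 lists AF in the first week, at discharge, and "atrial fibrillation at time of post-operative follow up", plus AF needing cardioversion or a new anti-arrhythmic drug. The form reproduced in Appendix E asks about AF at one week, AF at discharge, its treatment, and whether it had resolved by discharge. It has no AF field for the period after discharge and no AF onset date. Section 6.2.6 says follow-up data come from the records of standard-of-care visits, weekly for one month after discharge and then monthly through the first year.

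**The concern.** The two objectives differ only in their time window, so the second adds to the first only through what is learned after discharge. The protocol describes AF mainly as a complication of the post-operative course (sections 2.0 and 3.7), so index-stay events may well dominate the first-year count. A lower first-year rate could then be read as lasting prevention when it repeats the primary result. A late excess of AF on gel could also go unseen behind an in-hospital advantage.

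Section 4.2 says this pilot is meant to supply preliminary data for a larger randomized trial. Whether any benefit persists after discharge bears on that trial's endpoint and length of follow-up. If the records are abstracted without onset dates, the question cannot be settled later from the study database.

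**Working it through.** The plan gives no first-year AF rate to reproduce, so the check is a set of scenarios.

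**Inputs from section 14.1**
- Control in-hospital AF: "the reported rate of early atrial fibrillation post lung transplantation is approximately 30" per cent, so 0.30.
- Gel in-hospital AF: the plan is "assuming that the use of amiodarone gel will result in prevention of atrial fibrillation in 90% patients". This can mean 90% of patients stay AF-free (rate 0.10) or a 90% relative reduction (0.30 × 0.10 = 0.03). Both are used.

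**Assumption (not in the documents)**
- q is the risk of first AF between discharge and one year in patients without index-stay AF. It is varied from 5% to 30% and set equal in both groups, so there is no late effect. Deaths are ignored.

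**Formula.** First-year AF = p + (1 − p) × q, where p is the in-hospital rate. With equal q, the one-year difference is (p control − p gel) × (1 − q).

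**Worked case, q = 5%.** Control: 0.30 + 0.70 × 0.05 = 0.335. Gel at 0.10: 0.10 + 0.90 × 0.05 = 0.145. Gel at 0.03: 0.03 + 0.97 × 0.05 = 0.0785.

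| q, both groups | Control | Gel (p = 0.10) | Difference | Gel (p = 0.03) | Difference | Index-stay share of control events |
|---|---|---|---|---|---|---|
| 5% | 33.5% | 14.5% | 19.0 points | 7.9% | 25.7 points | 0.30/0.335 = 90% |
| 10% | 37.0% | 19.0% | 18.0 points | 12.7% | 24.3 points | 81% |
| 20% | 44.0% | 28.0% | 16.0 points | 22.4% | 21.6 points | 68% |
| 30% | 51.0% | 37.0% | 14.0 points | 32.1% | 18.9 points | 59% |

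Every difference in the table comes from the index stay.

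**Chance of a significant one-year result.** With 20 gel patients and 50 controls (section 4.2.3), the exact probability that a two-sided Fisher test at 0.05 (level assumed; the plan states none) favours gel is:
- q = 5%: 29% (p = 0.10) or 57% (p = 0.03)
- q = 10%: 25% or 47%
- q = 20% to 30%: 19% to 14%, or 34% to 24%

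For comparison, the same test on the in-hospital endpoint gives 33% or 71%.

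**Masking.** Let late AF be 20% on gel and 10% in controls, with p = 0.10 on gel. Gel: 0.10 + 0.90 × 0.20 = 0.28. Control: 0.30 + 0.70 × 0.10 = 0.37. Gel still looks 9 points better although its late risk is doubled. The one-year difference disappears only when gel late AF reaches (0.37 − 0.10)/0.90 = 30%.

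**What the data items can show.** AF present at a visit may have begun in hospital or since discharge. AF that starts and stops between visits need not be present at either. The cardioversion and new-drug items could catch treated late AF, but section 4.2.2 asks for no date and they miss untreated episodes. The form shown has nowhere to enter post-discharge AF. So the late component cannot be separated, and the first-year endpoint itself may be under-counted.

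**The case against.** The strongest reply is that the endpoint matches its objective. Both count the first year from transplant, and section 4.3.2 claims neither durability nor independence from the primary endpoint. Short and long windows nested in this way are ordinary. This stands: a reader might infer that the endpoint contradicts its objective or cannot answer it, and the text does not support that.

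A reader might also take the 14% to 57% above as a false-positive rate. It is not. First-year AF truly differs in those scenarios, so the figures are power for a real first-year difference, and they lie below the power for the in-hospital endpoint on the same inputs.

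Nor would the plan necessarily miss a gel that only delays AF. Under pure delay, in-hospital AF would be 10% against 30% and first-year AF would converge, for example at 30% in both groups. Comparing the two endpoints would show this if late AF were captured. What can be masked is partial delay or a moderate late excess.

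It is also tempting to cite section 3.4, "Due to the short half-life and one time application of the amiodarone gel", as proof that no late effect is possible. That sentence concerns residual risk, not duration of efficacy.

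Finally, replacing the endpoint with post-discharge AF, split by in-hospital AF, would bring its own bias. In-hospital AF is affected by treatment. If gel prevents it, AF-prone gel patients move into the AF-free stratum, which tilts that comparison against gel. This objection also stands and limits the fix.

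None of these replies answers the data-capture gap.

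**Conclusion.** The point holds as a limit on interpretation together with a gap in data capture; it is not a contradiction in the plan. The overlap follows from the wording of the two endpoints and needs no assumption. Its size does: with 30% in-hospital AF in controls, 10% or 3% on gel, and equal late risks of 5% to 30%, the index stay alone produces a one-year difference of 14 to 26 points. The late risks are assumptions, deaths are ignored, and the study is a pilot with no stated success criterion, so the figures illustrate and do not forecast.

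The firmest part is the data items: undated AF status at follow-up, and a form with no post-discharge AF field, can neither separate late from in-hospital AF nor fully measure the endpoint as defined. It is worth correcting because the correction is cheap.

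**What to change.** 1. Keep cumulative first-year AF as the secondary endpoint, and state in section 4.4.2 that it includes the index stay.
2. In section 4.2.2, replace AF status at follow-up with any AF since the last visit, with the date of first onset. Add a matching field to the Appendix E form. Take it from the same kind of medical record in both the gel and the historical cohort.
3. In section 14.1, add a descriptive report of AF from discharge to one year in each cohort, with its 95% confidence interval. Do not restrict first-year claims to this result, and do not compare the groups within strata defined by in-hospital AF.
4. State that the cumulative result will not be described as evidence of benefit after discharge.

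The cost is a little more record review, with no added visits because follow-up already comes from medical records. The historical records may be less complete, which should be reported. The late estimate will be imprecise: at an assumed 5% late risk, about 20 × 0.05 = 1 event on gel and 50 × 0.05 = 2.5 in controls even if every patient were at risk. That is why it should be descriptive only.

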### **4.5 INCLUSION AND EXCLUSION CRITERIA**

A subject, who meets all of the inclusion criteria, and none of the exclusion criteria, is eligible to participate in this study.

All subjects enrolled in the clinical study (including those withdrawn from the clinical study or lost to follow-up) will be accounted for and documented, assigning an identification code linked to their names, alternative identification or contact information.

A log with enrollment information will be kept up to date throughout the clinical study by the principal investigator or his/her authorized designee. To ensure subject privacy and confidentiality of data this log must be maintained throughout the clinical study at the clinical site.

To participate in this clinical study, the subject must meet all of the following inclusion criteria and none of the exclusion criteria:

#### Inclusion Criteria

- Subject or legal representative has signed Informed Consent Form (ICF)
- Undergoing lung transplant at the Jewish Hospital - Patients undergoing single or double lung transplantation at Jewish Hospital (Louisville, KY). Indications for transplantation will include: Idiopathic Pulmonary Fibrosis, COPD and Cystic Fibrosis. Patients requiring cardiopulmonary bypass (CPB) along with those not requiring CPB will be included
- Age  $\geq$  18 years
- Subjects willing and able to comply with the follow up requirements of the study

#### Exclusion Criteria

- Patients with previous history of atrial fibrillation
- Patients with previously document allergy or adverse reaction to amiodarone
- Patients with previous ablation for atrial fibrillation
- Patients with an implantable pacemaker
- Patients who are pregnant

## 4.6 SUBJECT POPULATION

### 4.6.1 Subject Screening

All subjects listed for lung transplant at the investigational site will be screened by a member of the investigational team previously trained on the CIP and delegated to do so.

Subjects who do not meet the inclusion/exclusion criteria will not be eligible to participate in this study.

Subjects meeting the inclusion/exclusion criteria will be fully informed about the study and invited to participate in the study. In case the subject agrees to participate, a duly signed and dated Subject Informed Consent Form/Authorization will be obtained.

### 4.6.2 Point of Enrollment

Subjects are considered in screening for the study when the subject has provided written Subject Informed Consent. (Refer to section 4.7 for the Informed Consent Process). Subjects are considered enrolled when they have the study intervention.

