## 1.0 SYNOPSIS

Title:	The Intra-Operative Application of Amiodarone Releasing Hydrogel to Prevent Postoperative Atrial Fibrillation in Patients Undergoing Lung Transplantation
Acronym:	AMGeL
Purpose:	The purpose of the study is to evaluate the intraoperative application of an amiodarone containing hydrogel for prevention of post-operative atrial fibrillation in lung transplant patients.
Objectives:	
Primary Objective: The purpose of the study is to evaluate the intraoperative application of an amiodarone containing hydrogel for prevention of post-operative atrial fibrillation in lung transplant patients.
 
Secondary Objective: Demonstrate safety and effectiveness of the amiodarone hydrogel application during lung transplantation in preventing atrial arrhythmias during first year of transplantation.

Endpoints:	
Primary Endpoint will evaluate: --Development of post-operative atrial fibrillation during initial hospitalization
 
Secondary Endpoints to be evaluated: --Length of Stay initial hospital stay -Development of post-operative atrial fibrillation during first year post transplant -Thirty-day survival -One-year Survival

Design:	
In Lung Transplant patients, we propose use of amiodarone hydrogel during surgery will result in reduced rates of post-op atrial fibrillation.
 
The expected total duration of the study is 24 months.
 
The clinical study will be conducted in 1 center in the United States.
 
20 subjects will be enrolled in this study.
 
The enrolled subjects will be compared to the historical controls who did not receive the amiodarone gel therapy during lung transplant surgery.
 
Subjects will be followed for 1 year.

Drug used:	Amiodarone Hydrogel in Coseal
Study Population	Male and female patients, age 18 years and older with end stage Lung Disease who require Lung Transplant.
Inclusion/Exclusion Criteria	
Inclusion Criteria
 
 
1) Subject or legal representative has signed Informed Consent Form (ICF)
 
2) Undergoing lung transplant at the Jewish Hospital
 
3) Age <math>\geq</math> 18 years
 

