	
4) Subjects willing and able to comply with the follow up requirements of the study
 
Exclusion Criteria
 
 
1) Patients with previous history of atrial fibrillation.
 
2) Patients with previously documented allergy or adverse reaction to amiodarone.
 
3) Patients with previous ablation for atrial fibrillation
 
4) Patients with an implantable pacemaker.
 
 
•

Data Collection
	
Subjects will be evaluated and enrolled for receiving the amiodarone gel during their waiting period for lung transplantation.
 
Patients who consent to be part of the study will receive the amiodarone gel during the surgery for lung transplantation. The amiodarone gel will be sprayed just after transplanting the lung(s). Patients will then be followed in-hospital until discharge and data regarding the primary study end-point will be captured.
 
Patient study visit follow-up will occur post-operatively as per standard of care after lung transplantation. Patients' follow-up is generally comprised of routine history and physical examination. These will provide sufficient data to address the secondary study end-points. All follow up data will be collected from the subject's medical records.
 
•

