### **4.2 STUDY DESIGN AND SCOPE**

This study will prospectively evaluate the use of an amiodarone releasing hydrogel applied to the pulmonary veins and atria at the time of lung transplantation. This study will include patients undergoing lung transplantation at Jewish Hospital, Louisville KY. The prospective group will be compared to historical controls from the same institution. We will access medical records and database entries for those patients undergoing lung transplantation after January 1st 2005 in order to obtain matched controls for analysis. Informed consent will be obtained from the prospective cohort prior to patient enrollment. This pilot study will be used to obtain preliminary data in order to proceed with a larger randomized, controlled trial.

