#### 6.2.4 Prior to lung transplant

When a consented subject is informed that they are scheduled for a lung transplant, the study team will review their medical record to confirm they are still eligible to participate in the study. If they meet any of the exclusion criteria since the initial consent was signed, they will be considered a screen failure and will not undergo the study procedure.

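### Gel patients enter the analysis only once the gel is on, but no matching landmark is set for the historical controls

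*Combined protocol and SAP*

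**What the plan says.** **Gel arm.** Section 4.6.2 separates two states. Up to the gel, "Subjects are considered in screening for the study when the subject has provided written Subject Informed Consent". After that, "Subjects are considered enrolled when they have the study intervention". The Synopsis (1.0, Data Collection) times the spraying to directly after implantation, so entry to the gel arm falls late in the operation. Section 14.1 then fixes the analysis set: "Endpoint analysis will be on “as-treated” basis as historical control data will be used".

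**Controls.** Section 4.2 draws on records of "those patients undergoing lung transplantation after January 1st 2005 in order to obtain matched controls for analysis". The Synopsis describes them as "historical controls who did not receive the amiodarone gel therapy during lung transplant surgery", and 14.1 adds: "The control arm is the historic controls and will use the previously treated lung transplant patients at the facility". Section 4.2.3 gives their number as 50. The plan names no matching variables and no time zero for controls. It does not ask that a control survived to, or was suitable for, the step at which gel would have been sprayed.

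**Other enrolment points.** The Synopsis has subjects enrolled while they wait for a transplant. Section 9.3 equates enrolment with the date the consent form is signed. Neither agrees with 4.6.2.

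**The concern.** Entry to one cohort depends on an event during surgery; entry to the other does not. In the gel arm, survival to the end of implantation is guaranteed by definition. In the controls it is not, because nothing excludes a patient who died on the table.

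Two kinds of patient can be lost on the gel side only: those who die before spraying, and those who are eligible but do not get the gel. The rest of the plan does not bring them back into the comparison. Section 4.5 promises an account of enrolled subjects, which under 4.6.2 means sprayed subjects. Adverse event reporting in 9.3 runs from the intervention.

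Thirty-day and one-year survival are named secondary endpoints (4.4.2), and both objectives in 4.3 claim safety. Section 4.2 says the data will be used to go on to a larger randomized trial. A survival figure that flatters the gel would be carried into that decision.

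**Working it through.** The plan gives no figure on this point to reproduce: it states no rate of death before spraying and no rate of omitted gel. The check is to set the entry rules side by side, then see what an inert gel would show under assumed rates.

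**1. Entry rules**

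| | Gel arm | Controls |
|---|---|---|
| Source | Consenting patients listed for transplant (4.6.1) | Records of transplants since January 2005 (4.2) |
| Number | At least 20 (4.2.3) | 50 (4.2.3) |
| Entry event | Gel applied (4.6.2), after implantation (1.0) | Transplanted without gel (1.0); no landmark |
| Death before spraying step | Not enrolled, so outside the as-treated set | Not excluded by any section |
| Eligible, gel omitted | Not enrolled, so outside the as-treated set | Comparable difficult operation not excluded |

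**2. Thirty-day mortality with an inert gel.** Let m be mortality counted from the start of surgery and d the part that falls before spraying. The gel arm shows (m − d)/(1 − d). Both inputs are assumptions.

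- m = 6%, d = 2 points: (0.06 − 0.02)/0.98 = 4.1%
- m = 6%, d = 4 points: (0.06 − 0.04)/0.96 = 2.1%
- m = 5%, a quarter or half of deaths before spraying: 0.0375/0.9875 = 3.8%; 0.025/0.975 = 2.6%
- m = 10%, same shares: 0.075/0.975 = 7.7%; 0.05/0.95 = 5.3%

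Apparent mortality can fall by about half or more, always in favour of the gel. In a group of 20 the largest of these shifts are (6.0 − 2.1) points × 20 = 0.8 patients and (10 − 5.3) points × 20 = 0.9 patients.

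**3. AF with an inert gel.** The overall rate of 30% is from 14.1. Let x be the share not sprayed and r their AF risk, both assumed. The gel arm shows (0.30 − x·r)/(1 − x).

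| x | r = 0 (die before AF can occur) | r = 50% | r = 70% |
|---|---|---|---|
| 5% | 31.6% | 28.9% | 27.9% |
| 10% | 33.3% | 27.8% | 25.6% |
| 15% | 35.3% | 26.5% | 22.9% |

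At x = 20% and r = 50% the result is (0.30 − 0.10)/0.80 = 25.0%. The sign depends on who is lost: high-risk survivors left without gel favour the gel, and deaths before AF could occur work against it. Most of these shifts are about one patient in 20 or fewer (5.0 points × 20 = 1.0). The extreme corner, x = 15% with r = 70%, gives 7.1 points, or 1.4 patients.

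**4. What a common landmark does.** If controls must also be alive at the end of implantation, their mortality in the first example becomes (0.06 − 0.02)/0.98 = 4.1%, equal to the gel arm, and the false difference is gone. The landmark does not repair selection through omitted gel among patients who survive implantation. Counting all patients taken to surgery does: at x = 10% and r = 50%, 0.90 × 27.8% + 0.10 × 50% = 30.0%.

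**The case against.** Several stronger readings are tempting, and the documents do not support them.

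- A reader might infer that controls are counted from the start of transplantation. No section says so. That is the natural reading of 4.2, but control time zero is undefined.
- A reader might take the controls to be every previous transplant patient. Sections 4.2 and 4.2.3 describe a matched set of 50.
- A reader might infer that early deaths in general drop out of the gel arm. Section 4.6.2 removes only deaths before spraying; a patient who dies afterwards is enrolled. Whether 6.4 (death as a withdrawal reason) together with the replacement rule in 14.1 removes later deaths is a separate question.
- A reader might say that unsprayed patients vanish without record. The Appendix E forms hold consent date, transplant date and gel volume, 8.2 requires the date and reason for every deviation, and 6.2.6 requires forms for consented patients who become ineligible. These patients can be traced. They are simply not in the comparison.
- A reader might cite 6.2.4, under which patients newly meeting an exclusion criterion before surgery are removed ("they will be considered a screen failure and will not undergo the study procedure"). That is an eligibility check before the operation, and an analysis of eligible patients would leave them out too.

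The broader defence is also fair. As-treated analysis is stated openly, no section allows the surgeon to leave the gel out, every size above is assumed, and this is a pilot whose sample size 14.1 says does not rest on a power analysis. All of that stands, and it limits the weight of the point. It does not supply a common time zero, and matching on baseline factors would not create one.

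**Conclusion.** The point holds in a limited form. Followed as written, the plan lets deaths before spraying and omitted gel leave the gel arm only, and this biases thirty-day and one-year survival toward the gel. For AF, the primary endpoint, the direction is uncertain, so a claim that the primary result is tilted toward the gel would go too far.

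The size cannot be known from the documents. Under the assumed ranges it is probably about one patient in 20 or fewer, and the AF shift is small beside the 20-point difference implied by 14.1 (30% against 10%, reading prevention in 90% of patients as an AF rate of 10%). Separately, the three enrolment points in the Synopsis, 4.6.2 and 9.3 contradict one another, whatever the size of the bias. Confidence is moderate: the asymmetry is plain from the text, but its effect rests on rates that nobody has stated.

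**What to change.** - In 4.6.2 and 14.1, set one time zero for both cohorts. Require controls to be alive at the end of implantation and to meet the same eligibility criteria, apart from consent and willingness to be followed, which cannot be applied to past records. Count survival and AF from that point in both cohorts.
- Reconcile the enrolment point across the Synopsis, 4.6.2 and 9.3.
- Report the numbers consented, taken to transplant and not given gel, with reasons. The gel volume field already exists; only the reason needs a place on the form.
- Keep the as-treated comparison, and add a sensitivity analysis that counts every consented, eligible patient taken to surgery, against controls counted from the start of surgery.

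The cost is some wording, one form item and a check of operative records for the controls. The sensitivity estimate is slightly diluted. With 20 sprayed patients at 10% AF plus 1, 2 or 3 unsprayed at 30%, the gel-arm rate is 2.3/21 = 11.0%, 2.6/22 = 11.8% or 2.9/23 = 12.6%. Power against 50 controls at 30% (two-sided 5%, normal approximation, both assumed) is 38%, 36% or 34%, compared with 40.5% if all are sprayed. If the unsprayed have 50% AF risk, the rates are 11.9%, 13.6% and 15.2%, and power is 34%, 29% and 25%. Since power is low in any case, this is a modest price for an analysis that is secondary.
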